7.8. METHOD OF BLINDING

The study design is double blind. The randomization list will be secured in a computer file with restricted access to only the designated personnel including those responsible for labeling and handling the study medication until the study database is locked and ready to be unblinded.

An analysis of Week 24 data, including the primary endpoint and bone mineral density endpoint will be performed after all subjects have completed Week 24 or terminated the study. The analysis will be performed by an unblinded statistician. The analysis will be restricted so that identification of individual patients is prevented as far as possible.

Every effort will be made to keep the Investigator and the subject fully blinded. Treatment allocation, individual P4 and E2 levels, Alkaline Hematin results (as of Study Day 1) will not be communicated up to the final Week 76 database lock.

7.9. EMERGENCY UNBLINDING

The study blind may be broken for an individual subject only in the case of an emergency when knowledge of the IMP is essential for the clinical management of the subject. The Investigator can break the blind for a subject by using the IWRS that permits immediate unblinding. In case of doubt as to whether emergency unblinding is necessary, the Investigator should contact the Sponsor prior to breaking the study blind.

In the case of a code break, the Investigator must inform the Sponsor immediately without revealing the code to the Sponsor study personnel and the complete Study Team.

If a Serious Adverse Event (SAE) is reported, the ObsEva (or delegate) Representative for Pharmacovigilance may unblind the treatment assignment for the affected subject. When applicable, an expedited report will be sent to all Investigators in accordance with regulations.

7.10. TREATMENT OF OVERDOSE AND MISUSE

An overdose is defined as any dose (i.e. quantity of drug given per administration or per day) above the maximum dosage defined in the protocol.

Misuse is the term used if more precise information is not available and additional information is needed to determine if there was a "medication error", "drug abuse" or "overdose".

Any details of overdose or misuse must be recorded in the eCRF.

Any case of overdose or misuse associated with an AE or a SAE must be reported as per the instructions detailed in Section 8.2.

The effects of an overdose of OBE2109 are unknown, but single and repeated doses of up to 400 mg were shown to be safe in a Phase 1 single and multiple ascending dose study, and doses up to 200 mg daily for 3 months were safe in endometriosis subjects (see Section 1.5).

7.11. OTHER SUPPLIES TO BE USED IN THE STUDY

The following items will be provided by the Sponsor free of charge to the subject:

- Iron supplementation (if applicable).
- Tampons and sanitary pads that are validated for the alkaline hematin method as well as a styrofoam box and containers to store used sanitary protection.
- Electronic Diaries will be used to record uterine bleeding IMP intake, UFS QoL, EQ-5D, pain NRS and PGI-I.
- Condoms with spermicide (or condoms and spermicide).
- Study bag to contain the items above

8. ADVERSE EVENTS AND SERIOUS ADVERSE EVENTS

Comprehensive assessments of any apparent toxicity experienced by the subject will be performed throughout the course of the study from the time of subject's signature of informed consent. Study site personnel will report any AE, whether observed by the Investigator or reported by the subject (see section 8.2.1, Eliciting Adverse Events).

The safety profile of OBE2109 will be assessed through the recording, reporting and analysis of baseline medical conditions, AEs, physical examination findings, vital signs, laboratory tests, and BMD assessments.

The reporting period for AEs is described in section 8.5.

8.1. ADVERSE EVENTS

8.1.1. Definitions

Adverse Event:

An adverse event (AE) is defined as any untoward medical occurrence in a clinical trial subject administered an investigational medicinal product (IMP) and which does not necessarily have a causal relationship with this treatment. It can therefore be any unfavorable sign (including an abnormal laboratory finding), symptom, or disease temporally associated with the use of an IMP, whether or not considered related to the IMP.

For screening failure subjects, adverse events and updates must be recorded in the eCRFs using the AE or SAE forms (as appropriate) until the date the subject is determined to be a screening failure. Beyond that date, only serious or medically relevant events will be followed up.

Severity:

The severity of AEs must be assessed by the Investigator according to the following definitions. The term "severity" is used to describe the intensity of a specific event. This has to be distinguished from the term "serious".

Mild:	The subject is aware of the event or symptom, but the event or symptom is easily tolerated (e.g. no reduction in daily activities is required).
Moderate:	The subject experiences sufficient discomfort to interfere with or reduce her usual level of activity.
Severe:	Significant impairment of functioning: the subject is unable to carry out usual activities and/or the subject's life is at risk from the event.

Causality assessment:

The causality assessment of an AE to the IMP will be rated as follows by the Investigator:

Not related:	There is no reasonable possibility of causal relationship between an AE and IMP.
Related:	There is at least a reasonable possibility of a causal relationship between an AE and an IMP. This means that there are facts (evidence) or arguments to suggest a causal relationship.

Unexpected Adverse Event:

Any AE which is not consistent in specificity or severity with the current Investigator's Brochure, including all amendments, is considered unexpected.

Outcome:

Outcome describes the status of the AE. The Investigator will provide information regarding the subject outcome of each AE, and the options include:

Fatal	Termination of life as a result of an AE.
Not recovered/not resolved	Subject has not recuperated or the AE has not improved.
Recovering/resolving	Subject is recuperating or the AE is improving.
Recovered/resolved	Subject has recuperated or the AE has resolved.
Recovered with sequelae/resolved with sequelae	AE has resolved, but the subject has symptoms or pathology
Unknown	Unknown, not observed, not recorded, or refused.

Action taken regarding study drug:

The Investigator will provide the action taken regarding study drug in response to each AE, and the options include:

Drug (study drug) interrupted	Study drug is being temporarily interrupted due to AE.
Drug (study drug) withdrawn	Decision was made to withdraw the study drug due to AE.
Unknown	Unknown, not observed, not recorded, or refused.
Not applicable	AE started before dosing or after dosing finalized.

8.1.2. Abnormal laboratory findings and other objective measurements

Abnormal laboratory findings and other objective measurements (e.g. vital signs) must be reported as an AE only if assessed by the Investigator as "clinically significant" e.g. meeting at least one of the following conditions:

- 1. The abnormality suggests a disease and/or organ toxicity AND this abnormality was not present at the Screening visit or is assessed as having evolved since the Screening visit.
- 2. The abnormality is a Serious Adverse Event.
- 3. The abnormality results in discontinuation of the IMP.
- 4. The abnormality requires medical intervention or concomitant therapy.

The Investigator must initial and date each laboratory report printouts and note directly on the report whether or not each out-of-range laboratory result is clinically significant. The outcome of this assessment will be reported using an AE or SAE form, if appropriate.

When reporting an abnormal finding for laboratory parameters or other objective measurements on the AE page of the eCRF, a clinical diagnosis should be recorded rather than the abnormal value itself, if available (for example, "anemia" rather than "decreased red blood cell count").

For all of these AEs, whether or not related to the treatment, the laboratory test(s) will be followed-up as appropriate.

8.1.3. Baseline Medical Conditions

Medical conditions present at the Screening visit(s), including results of the study screening assessments, are defined as Baseline Medical Conditions. These medical conditions should be adequately documented on the "Medical History" page of the eCRF. Baseline Medical Conditions that worsen in severity or frequency during the study should be recorded and reported as AEs.

8.1.4. Exacerbation of symptoms

In this protocol, symptoms and signs of exacerbation or worsening of heavy menstrual bleeding will usually be captured in the context of efficacy assessment. Therefore, symptoms, exacerbation or worsening of bleeding will NOT be considered as AEs nor captured on the AE page of the eCRF unless clinically significant AND not consistent with the anticipated natural progression of the disease. Lack of efficacy of the study drug is NOT considered as an AE.

8.1.5. Adverse Events of Special Interest

Not Applicable.

8.2. PROCEDURES FOR ELICITING, RECORDING AND REPORTING ADVERSE EVENTS

8.2.1. Eliciting Adverse Events

Data on AEs will be obtained at scheduled or unscheduled study visits, based on information spontaneously provided by the subject and/or through questioning of the subject.

To elicit AEs, questioning at each study visit should begin with simple non-leading questions. For example:

- How have you felt since your last visit?
- Have you had any health problems since you were here last?

If a subject is seen by a physician not involved with the study in relation to an AE, the Investigator should make every effort to contact the treating physician in a timely manner in order to obtain all information necessary for the appropriate reporting of the event.

8.2.2. Recording of Adverse Events in the eCRF

As the quality and precision of acquired AE data are critical, Investigators should use the AE definitions provided in the above sections and should follow this guideline when completing the AE pages of the eCRF:

- Whenever possible, recognized medical terms should be used to describe AEs rather than colloquialisms (for example, 'influenza' rather than 'flu'), and abbreviations should be avoided in provided AE term.
- AEs should be described using a specific clinical diagnosis, if this is available, rather than a list of component signs or symptoms (for example, 'congestive heart failure' rather than 'dyspnoea, rales and cyanosis').
- However, signs and symptoms that are not linked (as "co-manifestations") to an identified disease or syndrome, or for which an overall diagnosis is not available, should be reported as individual AEs in separate eCRF AE page(s).
- Provisional diagnosis (e.g. "suspected Myocardial Infarction") are acceptable but should be followed up with a definite diagnosis, if finally available.
- AEs occurring secondary to other events (e.g. sequelae or complications) should be identified by the primary cause. A primary AE, if clearly identifiable, generally represents the most accurate clinical term to record in the eCRF. The Investigator should be invited to provide his/her opinion of which is the primary AE.

8.2.3. Reporting of Adverse Events

Complete and accurate data on all AEs experienced for the duration of the reporting period, as defined in section 8.5, will be reported on an ongoing basis in the AE pages of the eCRF.

It is important that each AE report includes a description of the event, whether it is considered serious (and if so the criterion satisfied), its duration (onset and resolution dates), its severity, its relationship to the IMP(s), any other potential causality factors, any treatment given or other action taken (including dose modification or discontinuation of the IMP) and its outcome.

8.3. SERIOUS ADVERSE EVENTS

8.3.1. Definitions

A Serious Adverse Event (SAE) is defined as any untoward medical occurrence or effect that at any dose:

• results in death,

i.e. the AE causes or contributes to the death.

• is life-threatening,

i.e. the AE places the subject at immediate risk of death; it does not refer to an AE which hypothetically might have caused death if it were more severe.

• requires inpatient hospitalization or prolongation of existing hospitalization,

i.e. the AE requires at least an overnight admission or prolongs a hospitalization beyond the expected length of stay. Hospital admissions for surgery planned before study entry, for social reasons, for any elective surgery (i.e. plastic surgery) or for normal disease management (including treatment adjustment) are NOT to be considered as SAE according to this criterion.

• results in persistent or significant disability / incapacity,

i.e. the AE resulted in a substantial disruption of the subject's ability to conduct normal activities.

• is a congenital anomaly / birth defect,

i.e. an adverse outcome in a child or fetus of a subject exposed to the IMP before conception or during pregnancy.

• is an important medical event, i.e. is medically significant,

Medical and scientific judgment should be exercised in deciding whether an AE is serious in another situation. Important medical events that may not be immediately life-threatening or result in death or hospitalization but may jeopardize the subject or may require intervention to prevent one of the other outcomes listed in the definition above should also be considered serious. Examples of such events are intensive treatment in an emergency room, or at home for allergic bronchospasm, blood dyscrasias or convulsions that do not result in hospitalization, or development of drug dependency or drug abuse.

8.3.2. SAE Urgent Reporting Procedure

If a SAE occurs from subject consent up to Week 64, with the exception of a SAE related to BMD loss which will be reported up to Week 76, or, in case of study discontinuation, if the site becomes aware of an SAE up to 4 weeks post-study treatment discontinuation, regardless of relationship and expectedness, the Investigator is to take prompt and appropriate therapeutic action, if necessary, to protect the safety of study subjects and is to report such an SAE as follows:

For blinded studies, refer to section 7.9. for instructions related to emergency unblinding.

The Investigator must notify **VOISIN CONSULTING** (acting on behalf of ObsEva Pharmacovigilance) **WITHIN 24 HOURS** of awareness of a new SAE or of new information concerning a previously reported SAE (= follow-up).

To do so, the Investigator must complete a SAE report and any specific eCRF pages if justified by the protocol e.g. AE, medical history, concomitant medication eCRF pages and blinded and anonymized copies of any other supporting source documents such as lab reports, hospital discharge letter/report, etc.), sign it and send it directly to Voisin Consulting by e-mail using the dedicated e-mail address specified below:

Name/Title: Voisin Consulting / ObsEva Pharmacovigilance

E-mail: [contact]

VOISIN CONSULTING will notify ObsEva Pharmacovigilance within 1 working day after the receipt of the SAE form report or follow-up information, using the same reporting forms.

The SAE follow-up observation period, for the concerned subjects, will be jointly decided by the Investigator or one of the co-investigators (in case of Investigator's absence) and the Sponsor.

In addition, the Investigator must respond to any request for follow-up information or questions regarding the SAE the Sponsor may have, within 1 working day for urgent queries or 5 working days for normal queries. SAE will be followed until the Investigator and ObsEva agree that the event is satisfactorily documented and resolved/stabilized.

For any new SAE, the following minimum information is required as initial notification:

- Clear identification of the Investigator/Reporter with full contact information or site number,
- Subject identification details (study number, site number, subject's unique study identification number and date of birth),
- IMP(s) administration details (dose and dates),
- Diagnosis of the event (or a brief description of signs/symptoms/clinical course if the diagnosis is not available) and the date of onset,
- Seriousness criteria, see section 8.3.1,
- Causal relationship (Investigator's opinion) of the event with the IMP(s) or with the trial procedure (e.g. the causality according to the Investigator during screening).

8.4. **REPORTING TO THE INSTITUTIONAL REVIEW BOARDS AND REGULATORY AUTHORITIES**

The Investigator must comply with any applicable requirements related to the reporting of SAEs involving the study subjects to the IRB that approved the study.

ObsEva will comply with the applicable regulatory requirements related to the expedited reporting of suspected unexpected serious adverse reactions (SUSARs) to the regulatory authorities (e.g. Health Authority, Central IRB). The Sponsor will be responsible, through their US Agent, for notifying the FDA of any SUSAR, and the Sponsor or designee is responsible for notifying the Central IRB.

In accordance with ICH GCP guidelines, the Sponsor will inform the Investigator of "findings that could affect adversely the safety of subjects, impact the conduct of the trial or alter the IRB's approval/favorable opinion to continue the trial". In particular and in line with respective regulations, the Sponsor will inform the Investigator of AEs that are both serious and unexpected (i.e. as per the OBE2109 Investigator Brochure and SmPC for the Add-back) and are considered by the Investigator or the Sponsor, to have a reasonable possibility causal relationship between the administered IMP and the AE (i.e. SUSAR). The Investigator will keep copies of these safety reports in the investigator's file. National regulations with regards to safety reports notifications to Investigators will be taken into account.

Unless clearly defined otherwise by national or site-specific regulations, and duly documented, the responsible Investigator will promptly notify the concerned IRB of any safety reports provided by the Sponsor and provide copies of all related correspondence to the Sponsor. Only when specifically required by regulations, the Sponsor (or delegate) will provide appropriate safety reports directly to the concerned IRB and maintain records of these notifications.

8.5. **REPORTING PERIOD**

Adverse Events (AEs) are collected on an ongoing basis from the day of signed informed consent. All new AEs and updates on all ongoing AEs or AEs with an unknown outcome, must be recorded up to Week 64, with the exception of an AE related to BMD loss which will be reported up to Week 76.

A last batch of queries will be sent after the subject's last study visit if remaining ongoing/unknown outcomes of reported AEs are pending. After the last batch of queries with all collected data have been fully processed, eCRFs and the database will no longer be updated. Only SAEs and medically relevant ongoing/unknown outcome AEs will be followed-up until resolution or stabilization, under Voisin Consulting responsibility.

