3.2. SAFETY ENDPOINTS

- BMD assessed by dual-energy X-ray absorptiometry (DXA) for femoral neck, hip and spine at Weeks 24, 52 and 76.
- Frequency and severity of treatment-emergent adverse events (TEAEs).
- Any clinically significant changes from baseline in clinical laboratory assessments: hematology, coagulation parameters, chemistry, lipids and serum hormones.
- Any pathological changes from baseline in the endometrium as assessed by histology from endometrial biopsies performed at Weeks 24 and 52.
- Change from baseline in any other safety parameter including weight, vital signs, gynecological assessment, breast assessment and endometrial thickness.

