6.2.3.1. Study Visit Week 64 ± 7 days

The following tests and evaluations will be performed at the Week 64 Study Visit:

- Previous and concomitant treatments recording
- AE recording
- Physical examination (including weight)
- Vital signs (blood pressure and heart rate)
- Gynecological examination
- TVUS of uterus and ovaries including: uterus dimensions, myoma dimensions, endometrium thickness and assessment of ovaries
- Endometrium biopsy if the Week 52 biopsy was not assessable, not done or diagnosis was not benign. If no tissue is available, the biopsy should be repeated as soon as possible in the following days
- Blood samples for hematology, coagulation parameters, chemistry, lipids, hormones (E2, P4, FSH (if menstruations have not returned)). The subject must be fasting for the lipid blood sample
- Contraception counseling (not applicable in case of tubal ligation)
- Urinary protein dipstick
- Urine pregnancy test
- eDiary check for good completion
- Pain NRS, PGI-I, UFS QoL and EQ-5D questionnaires will be completed in the diary at site

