6.2.3.2. Study Visit Week 76 \pm 7 days – End of Follow-up Visit

The following evaluation will be performed at Week 76 Study Visit:

- BMD assessed by DXA for femoral neck, hip and spine. DXA can be performed ± 10 days from study visit
- AE recording if related to BMD loss
- Previous and concomitant treatments recording only if treatments with potential impact on BMD
- Urine pregnancy test
- Completion of the eCRF exit form

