b) The investigator and subject agree that at end of treatment all necessary actions will be taken to get a sufficient endometrium sample (e.g. short anaesthesia, if necessary)

c) The medical monitor of the study approves the randomization of the subject.

If biopsy samples collected during the study are inadequate and cannot be analysed by the laboratory they must be repeated as follows:

- Week 24 biopsy must be repeated at Week 36
- Week 52 biopsy must be repeated as soon as possible

- Week 64 biopsy must be repeated as soon as possible

In case of endometrial hyperplasia without atypia, the biopsies taken at Weeks 24, 52 and 64 must be repeated. In case of endometrial hyperplasia with atypia or in case of neoplasma, the laboratory will send an alert and the medical monitor will contact the sites to discuss the proceeding in line with local practice.

In case of dilatation and curettage during the study, which will be by definition a SAE, pathology results will be requested as part of the SAE follow-up information.

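### AE and SAE recording closes at Week 64 for everything but bone loss, while the protocol orders repeats of Week 64 endometrial biopsies and defines curettage during the study as an SAE

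*Protocol*

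**What the plan says.** **Recording windows.** Section 8.5 requires that new AEs and updates "must be recorded up to Week 64, with the exception of an AE related to BMD loss", the bone exception running to Week 76. Section 8.3.2 applies the same limit to urgent reporting: "If a SAE occurs from subject consent up to Week 64, with the exception of a SAE related to BMD loss". For early discontinuation it adds a limit based on awareness: "if the site becomes aware of an SAE up to 4 weeks post-study treatment discontinuation". The Week 76 visit list (section 6.2.3.2) has only "AE recording if related to BMD loss", and footnote o of Appendix A agrees.

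**Biopsies.** Section 6.2.3.1 calls for a Week 64 biopsy "if the Week 52 biopsy was not assessable, not done or diagnosis was not benign". Section 6.4.4 then says of samples the laboratory cannot analyse: "Week 64 biopsy must be repeated as soon as possible". For hyperplasia without atypia, "the biopsies taken at Weeks 24, 52 and 64 must be repeated". The same section treats dilatation and curettage during the study as an SAE by definition, with pathology requested in the SAE follow-up.

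**Endpoint.** Section 3.2 lists pathological endometrial change "assessed by histology from endometrial biopsies performed at Weeks 24 and 52". The synopsis names the same two weeks.

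**The concern.** The protocol keeps looking for endometrial pathology after the point at which it stops recording new events other than bone loss. A repeat of a Week 64 biopsy normally follows a central laboratory result on a sample taken at that visit, so its own result comes later still. Bone loss, the other safety outcome still pursued after treatment, was given an extension to Week 76; endometrial pathology was not.

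At stake is whether a new endometrial diagnosis, found by a procedure the protocol ordered, has a defined place in the AE and SAE data. The women concerned are those in whom it matters most, because their Week 52 histology was missing, unusable or not benign. Section 6.2.1 also allows randomization without screening histology after failed attempts, so for some women a repeat of the Week 64 biopsy could be the only assessable sample in the study.

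**Working it through.** No sample-size or power figure is involved. The check is arithmetic on study weeks, then a reading of the sections against one another.

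**Weeks** (from sections 4, 6.2.2.8, 6.2.3 and 8.5)
- End of treatment to closure of general AE recording: 64 − 52 = 12 weeks.
- Closure to end of follow-up: 76 − 64 = 12 weeks.
- Total follow-up: 76 − 52 = 24 weeks. General collection is therefore closed for 12 of 24 weeks.

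**Which repeats meet the closure** (section 6.4.4)
- An inadequate Week 24 sample is repeated at Week 36, inside the window.
- An inadequate Week 52 sample is repeated as soon as possible, so normally inside the window.
- A Week 64 sample found inadequate, or showing hyperplasia without atypia, is repeated with no end date. This repeat will normally fall after closure.

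**What the text provides in each case**
1. *Week 64 sample inadequate, diagnosis first made on the repeat.* This is a new event not related to bone, after Week 64. Sections 8.5 and 8.3.2 do not include it, and the Week 76 visit does not ask for it.
2. *Hyperplasia without atypia on the Week 64 sample, repeat shows the same or better.* The finding can be dated to Week 64 and recorded. Section 8.5 then provides a last batch of queries after the last visit for pending outcomes, and follow-up of medically relevant AEs. This case is covered.
3. *As case 2, but the repeat shows atypia or neoplasm.* On the natural reading this is a new diagnosis outside the window. The protocol does not say whether it could instead be entered as an update of the recorded event.
4. *Curettage between Week 64 and Week 76.* Section 10.1.4 ends the study at the final database lock after the last Week 76 visit, so this is during the study and an SAE under section 6.4.4. Section 8.3.2 stops SAE reporting at Week 64 unless the event is bone-related. The two sections contradict each other.

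**Other routes into the data**
- The laboratory alert in section 6.4.4 covers atypia and neoplasm and leads to contact between medical monitor and site. It creates no AE or SAE entry and does not cover hyperplasia without atypia.
- The histology endpoint in section 3.2 stops at Week 52, so a result from Week 64 or later belongs to no listed endpoint.
- From Week 64, section 6.5 records only concomitant medication that may affect bone, so treatment of an endometrial finding would not show there either.
- The early-discontinuation limb of section 8.3.2 closes 4 weeks after treatment stops and does not extend the window for these findings.

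**The case against.** The strongest reply is that the gap is narrow and the sponsor would not be blind to it. Biopsies are read centrally by blinded pathologists, so histology has a data stream that does not depend on the AE page. Section 8.3.2 turns on when an SAE occurs, and the initial report asks for a date of onset, so a lesion diagnosed soon after Week 64 might be dated earlier. Section 6.2.3.1 says that where no tissue is obtained the biopsy is repeated within days, and with a visit window of ±7 days that can be read as completing the Week 64 assessment. Closing general collection 12 weeks after treatment and then collecting selectively is also a legitimate design.

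Much of this stands. It disposes of three stronger readings that a reader might infer:
- *Hyperplasia seen at Week 64 would be left without an outcome.* Section 8.5 does not support this: pending outcomes are queried after the last visit, and medically relevant events are followed to resolution or stabilization.
- *These findings would be missing from expedited reporting.* Section 8.4 binds the sponsor to the applicable rules with no Week 64 limit.
- *Atypia or cancer would be lost altogether.* The central reading and the alert would bring it to the sponsor.

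What the reply does not supply is a recording duty. Back-dating is left to whoever completes the form. The reading about days covers an absence of tissue evident at the visit, not a sample later judged inadequate by the laboratory. Neither point resolves the contradiction over curettage.

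**Conclusion.** The point holds as a gap and a contradiction in the recording rules. Three kinds of event fall outside the stated AE and SAE windows although section 6.4.4 seeks or defines them: a diagnosis first made on a repeated Week 64 biopsy, a progression found on such a repeat to atypia or neoplasm, and a curettage after Week 64. Results from Week 64 onward are also outside the histology endpoint.

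The size cannot be given as a number of women. The protocol states neither how often a Week 64 biopsy will be needed nor how often a sample is inadequate, and any count would be invention. What can be said is that the closed period is half of the follow-up, 12 of 24 weeks, and that cases are likely to be few. The conclusion assumes that Week 64 in sections 8.5 and 8.3.2 means the Week 64 visit, and that a diagnosis is dated to the sample on which it was first made. It is worth correcting because it costs little, not because it threatens the trial's main conclusions.

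**What to change.** - In sections 8.5 and 8.3.2, the Week 76 visit list (section 6.2.3.2) and footnote o of Appendix A, widen the exception to: AEs/SAEs related to BMD loss, or to an endometrial biopsy finding or curettage (including Week 64 biopsies and their repeats), reported up to Week 76.
- In section 3.2 and the synopsis, add Week 64 biopsies and all repeat biopsies to the histology endpoint.
- State in section 8.5 whether progression on a repeat biopsy is entered as a new event or as an update of the one already recorded.

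The cost is a few words in each place and slightly longer targeted AE collection. The Week 76 visit and the AE page already exist. No new visit, procedure or clinical rule is needed.
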